## HARP Assay: Hysteroscopy Anesthesia for Relief of Pain

#### Introduction

Ambulatory hysteroscopy is a diagnostic technique commonly used in gynecology for the evaluation of the female reproductive tract, especially for the detection and treatment of intrauterine pathology. Although generally well tolerated, the management of pain associated with this procedure remains a relevant concern for many patients. Proper pain control is critical to improving the patient experience, reducing anxiety, and avoiding complications related to discomfort during the procedure. Pain, among other factors, is precisely one of the main reasons for failure of the procedure (Pascual Pedreño et al., 2021).

## Justification of the relevance of the study.

In recent years, several studies have addressed pain control in hysteroscopy, many of which have explored the use of local anesthesia to relieve pain during the intervention (Nowak et al., 2024). However, despite systematic reviews and meta-analyses on the effectiveness of these interventions, evidence in this field remains limited and scattered, especially with regard to well-designed, controlled clinical trials (Ahmad et al., 2017). For example, although some studies have shown that intracervical anesthesia significantly reduces pain during hysteroscopy, heterogeneity in pain assessment methods, the type of anesthesia used, and patient characteristics make it difficult to generalize the results (Cooper et al., 2010; De Silva et al., 2020).

In addition, Cochrane reviews show that there is a lack of sufficient evidence to show that different anaesthesia modalities have significantly different effects or whether anaesthesia is actually beneficial in all cases (Cochrane, 2020). The 2021 clinical practice guideline of the Spanish Society of Gynecology and Obstetrics (SEGO) recommends the use of anesthesia only when hysteroscopes larger than 5 mm are used, with a low quality of evidence. In this same document, it is highlighted that, although the differences found in other studies are statistically significant, they do not seem to be clinically relevant for the reduction of pain during the procedure or at 30 minutes post-procedure, since the differences are small and do not reduce the number of vagal symptoms (Pascual Pedreño et al., 2021). These differences are more significant in postmenopausal women, highlighting the need for a higher-quality randomized clinical trial that provides strong evidence on the benefits of pain management during hysteroscopy.

Some national surveys, such as the one conducted by Huang et al. (2023), reveal that only slightly more than half of hysteroscopies are performed under anesthesia, underscoring the disparity in clinical practice globally. In neighbouring countries, several authors have already pointed out this variability in the application of anaesthesia and suggest the need to establish clear recommendations through national and international guidelines (De Silva et al., 2020).

Although some previous studies have identified a moderate reduction in pain with local anaesthesia, the biases inherent in many of these studies, such as lack of masking, non-randomised design, or variability in anaesthesia techniques, limit the validity of their conclusions. These biases can lead to an overestimation of treatment effects, highlighting the importance of a well-designed, blinded clinical trial for more reliable results. In addition, pain is a subjective phenomenon influenced by psychological factors, such as anxiety, previous experience of pain, or the patient's expectations, which increases the complexity of its assessment. Without proper control for these factors, studies can be affected by expectation bias or measurement bias.

Ambulatory hysteroscopy is proposed as a cost-effective technique compared to that performed in the operating room, however, the discomfort and poor tolerability of the test affects a non-negligible number of patients, who, due to pain, require it to be performed under sedation in the operating room (Smith et al., 2021). This fact highlights the urgent need to improve the experience of patients in outpatient procedures through more effective pain management techniques.

## Importance of a well-designed clinical trial.

A well-designed randomized clinical trial has the ability to reduce biases and provide more robust evidence on the efficacy of interventions, such as anesthesia, in reducing pain during hysteroscopy. In this sense, the study design should include a representative sample of patients, a standardized method of pain assessment (such as the VAS scale), and strict control of confounding variables that may influence pain perception, such as the professional's experience, previous anxiety, and the type of intervention.

Through a more rigorous design, the study will also be able to identify predictors of pain and contribute to the development of evidence-based recommendations for pain management in hysteroscopy. This evidence is critical, as it not only improves the quality of the procedure, but also has the potential to optimize the patient experience, improving treatment adherence and reducing the need for general anesthesia.

In addition, variables that will give rise to new hypotheses will be included, such as the "indication of surgical hysteroscopy for pain". Knowledge of this data will allow later, according to the results obtained in the trial and after analysing the costs per procedure, to carry out new cost-effectiveness studies and assess whether anaesthesia can really be an efficient strategy in the face of non-application of anaesthesia.

For all these reasons, this study is of great relevance for the field of gynecology and ambulatory surgery, since it will specifically address the gaps in the existing literature on pain management during hysteroscopy, strengthening the quality of the evidence in this field. This is essential to improve clinical practice, offering a solid basis for decision-making in pain management in outpatient gynecological procedures.

## Objectives of the study

The aim of the study is to demonstrate whether locoregional anaesthesia has an impact on the pain perception of patients who undergo ambulatory hysteroscopy, i.e. to demonstrate whether there are significant differences in pain perception in patients who undergo such anaesthesia and those who do not.

H0: Half pain (VAS) analgesia = half pain (VAS) without analgesia

As secondary objectives, if differences are demonstrated, we will try to show which variables interfere with the patient's pain through a logistic regression analysis.

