## Selected variables

The following variables are proposed to control for those factors that could influence pain perception during the procedure or that could be useful for further subgroup analysis. In addition, some variables are included to ensure the security of the procedure and the confidentiality of the data.

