## Variables of post-procedure pain

- VAS Scale (Visual Analog Scale) (Type of variable: Continuous quantitative) Range 0-10. To measure the intensity of the pain experienced by the patient.
- **Need for post-procedure analgesia** (Type of variable: Qualitative dichotomous) Yes/No. And **type of pain reliever used**.
- Size of the speculum Used (Type of variable: qualitative) (Small/medium/large). May influence the overall pain of the procedure
  - **Complications** (Type of variable: Qualitative dichotomous) Yes/No. Complications that occur during or after the procedure will be recorded.
  - **Complication Type** (Variable Type: Open-Label Qualitative) Details about the nature of the complication (if any).
  - **Indication for surgical hysteroscopy due to pain** (Type of variable: Qualitative dichotomous) Yes/No. If additional surgical intervention is required after hysteroscopy.

In addition, the patient's medical and personal history, as well as allergies, will be collected in the Medical Record to determine if there are contraindications to the procedure. All previously established inclusion and exclusion criteria will also be explored.

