## Sample size calculation

Variables used in the calculation.

**Primary study endpoint**: Pain measured using the VAS scale (0-10).

Since we compared two groups (with anesthesia vs. without anesthesia) on a continuous quantitative variable (VAS), we will use a Student's t-test for independent samples (or Mann-Whitney U if the distribution is not normal).

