## **Clinically Relevant Difference:**

• In previous studies, a reduction of at least 1.3 - 1.5 points in VAS has been considered to be clinically meaningful in gynecological procedures. □ Proposal: Establish an expected difference of 1.5 points in the VAS.

**Standard deviation** of pain in hysteroscopy without anesthesia:

According to previous studies, the standard deviation of pain ranges from 1.8 to 2.5 points in VAS.

Proposal: Use a standard deviation ( $\sigma$ ) of 2.0 for the calculation.

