#### **Final Estimate**

To calculate the sample size in a clinical trial comparing pain in two groups (with and without anesthesia), we used the formula to compare two independent means. The effect size (Cohen's d) is obtained by dividing the clinically relevant difference by the standard deviation, obtaining a moderate-high effect size according to Cohen's classification.

Using a t-test for two independent samples, the sample size that provides the desired power is sought. When the information is entered into sample size calculation software, the result is a sample size of 29 patients per group. This means that the study will need a total of **58** patients.

If follow-up losses are anticipated, it is recommended to increase the sample size by 10-20%. Therefore, it would be advisable to include between **64 and 70 patients** in total to ensure adequate statistical power.

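### The predictor analysis is a logistic regression with no binary outcome named, although pain is a continuous VAS, and it runs only if the primary comparison shows a difference

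*Protocol*

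**What the plan says.** - **Objectives of the study.** The null hypothesis is equal mean VAS in the two groups. The secondary objective is: "if differences are demonstrated, we will try to show which variables interfere with the patient's pain through a logistic regression analysis". No dependent variable or cut-off is given, here or elsewhere.
- **Importance of a well-designed clinical trial.** The aim appears without any condition: "the study will also be able to identify predictors of pain".
- **Selected variables.** The purpose of collecting them is stated as: "The following variables are proposed to control for those factors that could influence pain perception during the procedure".
- **Variables of post-procedure pain.** The VAS is typed as continuous quantitative, range 0-10, with the purpose "To measure the intensity of the pain experienced by the patient". Two pain-related items are Yes/No: need for post-procedure analgesia, and "Indication for surgical hysteroscopy due to pain". Neither is linked to the regression.
- **Sample size calculation.** For the primary comparison, "we will use a Student's t-test for independent samples (or Mann-Whitney U if the distribution is not normal". The expected difference is 1.5 points (1.3 to 1.5 is called clinically meaningful) and the SD used is 2.0, although "the standard deviation of pain ranges from 1.8 to 2.5 points in VAS". Alpha is 5%, power 80%, and "the result is a sample size of 29 patients per group".
- **Data Analysis, 3.1 to 3.4.** These cover a per-protocol analysis, subgroups (age, parity, type of pathology, other factors), a descriptive comparison and masking. They contain no regression. The subgroup analysis carries no condition and names no method.

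**The concern.** Two things are fixed badly.

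**The model class.** In its ordinary binary form, logistic regression needs a two-level outcome. The outcome named is the patient's pain, which this protocol measures on a continuous scale. A reader cannot tell what would be modelled. If the VAS were split, information already collected would be thrown away.

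**The condition.** Whether anxiety, age or parity predicts pain is a separate question from whether anaesthesia lowers it. Tying the first to a positive answer on the second means the predictor model is lost when anaesthesia works but the test misses it, and nearly always when it does not work. In that second case clinicians would still want to know who has most pain. The condition also conflicts with the unconditional aim in the rationale and with the stated reason for collecting the variables.

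**Working it through.** **1. The protocol's own sample size.** Inputs from the sample size section: difference 1.5, SD 2.0, alpha 0.05, power 0.80, 1:1 allocation. The test is read as two-sided, since the null hypothesis is equality.

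d = 1.5/2.0 = 0.75. Normal approximation: 2 × (1.960 + 0.842)² / 0.75² = 27.9, so 28 per group. Noncentral t: 28.90, so 29 per group, with power 0.801. The stated 29 is reproduced. A one-sided test would need 23, which supports the two-sided reading.

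**2. How often the condition skips the model.** The model runs only if the primary test is significant, so P(skipped) = 1 − power. Power comes from a noncentral t with 2n − 2 degrees of freedom and noncentrality d × √(n/2). At the design values: 0.75 × √14.5 = 2.856, critical value 2.003 on 56 df, power 0.801, skipped 0.199.

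| Difference | SD | d | Per arm | Model skipped |
|---|---|---|---|---|
| 1.5 | 1.8 | 0.833 | 29 | 12.3% |
| 1.5 | 2.0 | 0.750 | 29 | 19.9% |
| 1.5 | 2.5 | 0.600 | 29 | 38.8% |
| 1.3 | 1.8 | 0.722 | 29 | 22.9% |
| 1.3 | 2.0 | 0.650 | 29 | 31.8% |
| 1.3 | 2.5 | 0.520 | 29 | 50.5% |
| 1.5 | 2.0 | 0.750 | 32 | 16.0% |
| 1.5 | 2.0 | 0.750 | 35 | 12.9% |
| 0 | any | 0 | 29 | 95% |

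The 32 and 35 per arm rows apply if all 64 or 70 patients were evaluable.

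**3. What this does to finding a predictor.** The protocol gives no correlation between any variable and VAS, so r is an assumption. Simulation set-up: 58 patients, arm effect 1.5, within-arm SD 2.0, control mean 5.5 (assumed), VAS recorded to 0.1 and limited to 0-10. The model contains arm and one predictor. The ordinal model uses VAS rounded to whole points.

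Power for the predictor at r = 0.3 (5000 runs; the primary test was significant in 0.802):

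| Model | Always run | Run only if primary significant |
|---|---|---|
| Linear | 0.635 | 0.505 |
| Ordinal logistic | 0.631 | 0.502 |
| Binary logistic, median split | 0.451 | 0.355 |

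As a rough check, the conditional column should be near the product with 0.802: 0.635 × 0.802 = 0.509, 0.631 × 0.802 = 0.506, 0.451 × 0.802 = 0.362.

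At r = 0.4 (2000 runs, always run) the powers are 0.883 linear, 0.874 ordinal and 0.683 median split. At r = 0 the rejection rates are 0.050, 0.054 and 0.062, so the comparison is fair.

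**4. Reading the table.** The condition costs about 13 percentage points (63% to 50%) with a linear or ordinal model. The median split costs about 18 points (63% to 45%), but only if that is what logistic means here. Both together: 63% to 36%.

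**The case against.** **The outcome and coding may sit in an SAP that is not shown.** True for the cut-off and the covariate list, and their absence is not criticised here. But the protocol itself fixes the model class and the condition. An SAP could remove the condition only by departing from the stated objective.

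**The protocol never says the VAS will be split.** This stands. A reader might infer that a split VAS is planned and take the 45% and 36% figures as the consequence. The text does not support that. Ordinal logistic regression would need no split and loses almost nothing (0.631 against 0.635), and binary logistic regression would suit either Yes/No item. The split figures belong to one reading only.

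**Factors are examined without condition under Analysis by Subgroups.** This also stands in part. A reader might conclude that those analyses cannot consider several factors together. No method is stated, so that would be inferred from silence. What can be said is that the regression is the only multivariable model described.

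**Making a secondary analysis depend on the primary is a common cautious choice.** It can protect confirmatory claims. This objective is worded as an attempt to show what matters, makes no confirmatory claim, and the protocol gives no such reason. It is fair to add that the 20% is simply the planned type II error, and that 51% pairs the smallest difference with the largest SD.

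**Conclusion.** The point holds for the secondary objective. The protocol names a model class that does not evidently fit its continuous endpoint, and makes its only described multivariable model depend on a result that has no bearing on the question.

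The firm figures are those for skipping: 20% at the design values, 12-51% over the protocol's own ranges, 95% if anaesthesia has no effect. They use only protocol inputs and assume the t-test rather than the Mann-Whitney alternative. The fall in detection from about 63% to 50% rests on an assumed r of 0.3 and the simulation settings above. The further fall to 36% also requires a median split, which the protocol does not state.

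None of this touches the primary comparison: the t-test is valid and 29 per arm is correct. The matter should be corrected, but it is exploratory in weight.

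**What to change.** 1. Delete the condition on demonstrated differences from the secondary objective.
2. Replace the logistic regression with a linear model of VAS on arm plus a short pre-specified list of pre-treatment variables, for example STAI score, age and vaginal parity. Report it as exploratory whatever the primary result, with an ordinal logistic model of VAS as a sensitivity analysis. The list must be short: Patient variables and Procedure variables hold 14 + 10 = 24 entries (ID left out, BMI counted once), and 58/24 = 2.4 patients per entry. The protocol does not say that all would enter.
3. Keep binary logistic regression only for a Yes/No item that is named as its outcome.
4. Keep variables that arise during the procedure (duration, cavity entries, bipolar use, biopsies) out of any model meant to estimate the treatment effect.

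A STAI-adjusted treatment difference is optional and supporting only. Simulated power is 79%, 81% and 83% at r = 0.1, 0.2 and 0.3, against 80.1% unadjusted, so little gain is to be expected.

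Cost: no new data, visits or patients. The covariate list must be fixed before the data are seen, and STAI kept as a numeric score although anxiety is typed as ordinal. The change is an amendment needing prior ethics committee authorisation under Specific Commitments, item 1.

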#### Possible limitations

The anesthesia used in this study involves the administration of injections into the uterosacral ligaments, which makes masking difficult for the patient, as she is likely to be aware of such an intervention. A double-blind design is not possible, as the doctor administering the anaesthesia knows whether or not he is administering it. In addition, in a single-blind placebo design (such as saline), there may be difficulties in masking the procedure, as the simple sensation of the injection could influence the patient's perception of pain. Therefore, irrigation of the vagina and cervix with saline solution of saline solution will be proposed, simulating the application of local anesthesia, without injecting it.

The fact that the study does not employ a blinded design, either for the patient or for the physician, introduces certain limitations and potential biases. However, some of these biases are controllable and can be minimized with specific measures. For all these reasons, biases associated with the lack of masking can be incurred. These biases that need to be addressed are the ones mentioned below

#### **Expectation Bias (Placebo/Nocebo Effect):**

If the patient knows that she has received anesthesia, she may underestimate her pain, believing that the medication will relieve the symptoms.

☐ If the patient knows that she has not received anesthesia, she may overestimate her pain due to anticipation.

#### **Observer Bias:**

If the doctor in charge of assessing pain knows the group to which the patient belongs (anesthesia or non-anesthesia), he could subtly influence how he collects the data (for example, by showing greater empathy or being less rigorous in control).

#### **Selection Bias:**

If randomization is not performed strictly, inhomogeneous patient selection may occur, which would affect the validity of the results.

#### Other Limitations:

## Variability in pain perception

Pain is a subjective experience, influenced by psychological, emotional, and physical factors. Individual variability in pain perception can introduce difficulties in standardizing results. Factors such as anxiety, pain history, patient expectations, and personal tolerance can significantly influence the perception of pain during the procedure.

## Clinical and technical factors:

The experience and skill of the practitioner performing the hysteroscopy can influence the pain levels experienced by the patient. The technique used, the selection of equipment (e.g., the type of hysteroscope used), and the duration of the procedure may also be factors affecting the experience of pain, making it difficult to generalize the results.

#### Limitations in the control of external variables:

Although attempts will be made to control for factors that may influence pain (such as anxiety and the practitioner's level of experience), it is not possible to guarantee that all external variables will remain constant throughout the study. This could lead to variability in the results.

## Limited sample size:

Depending on the number of patients available to participate in the study, the sample size may not be large enough to detect significant differences between groups, which may limit the statistical validity of the results.

## **Protocol compliance:**

Although participants and practitioners will be instructed on the study protocol, there may be variability in adherence to the study, especially in data collection or implementation of interventions, which could introduce additional biases.

Given the above, it has been decided to carry out the clinical trial without blinding. However, strict variables that may influence the perception of pain should be established and should be carefully collected and controlled during the study to minimize biases as much as possible.

## Selected variables

The following variables are proposed to control for those factors that could influence pain perception during the procedure or that could be useful for further subgroup analysis. In addition, some variables are included to ensure the security of the procedure and the confidentiality of the data.

#### Patient variables

- **ID:** Identification number of the patient in the study (Type of variable: Nominal qualitative) Allows the pseudonymization of the data.
- **Age** (Variable Type: Continuous Quantitative) The age of the patient, as it can influence the perception of pain.
- **Allergies** (Variable Type: Nominal Qualitative) All allergies relevant to the procedure will be recorded.
- **Position of the uterus** (Type of variable: Nominal qualitative) Anteversion / Retroversion / Indifferent.
- **BMI** (Variable Type: Continuous Quantitative) May have some relevance to the overall pain associated with the procedure, e.g. when placing the speculum.
- **Parity** (Variable Type: Discrete Quantitative) Number of previous vaginal deliveries, as it can influence cervical dilation and pain during the procedure.
- **Previous interventions on the uterus** (Type of variable: Nominal qualitative) Includes cesarean sections, curettages, myomectomies, among others.
- **Previous interventions on the cervix** (Type of variable: Nominal qualitative) Includes conization, curettage, biopsy with diathermy loop, among others.
- **Age of menopause** (Variable type: Continuous quantitative) Menopause could influence pain tolerance due to hormonal changes.
  - **Taking oral contraceptives (OCC)** (Type of variable: Qualitative dichotomous)
  - Yes/No. The use of hormonal contraceptives can affect endometrial thickness and uterine sensitivity.
- **Time of the cycle** (Type of variable: Nominal qualitative) First phase / Second phase / Menstrual.

- **Body Mass Index (BMI)** (Variable Type: Continuous Quantitative) Obesity is associated with increased systemic inflammation, which may increase the perception of pain.
- **Previous dysmenorrhea** (Type of variable: Qualitative dichotomous) Yes/No. Patients with a history of painful periods may experience increased pain during hysteroscopy.
- **Polycystic ovary syndrome** (**PCOS**) (Variable type: Qualitative dichotomous) Yes/No. Associated with increased cervical resistance, which could make the procedure more difficult and increase pain.
- **Anxiety or fear of the procedure** (Variable type: Ordinal qualitative) Will be assessed using the STAI Anxiety Scale (State-Trait Anxiety Inventory) before the procedure.
- Taking chronic pain mediation may influence outcomes

